4.10.10 Assessment of AF Recurrence

Assessment of AF Recurrence will be completed at the 3M, 6M, 12M and 24M follow-up visits viaevaluation of 12 lead ECG recordings, holter monitoring and/or event recorder results. Subjects will be provided 7-day holter monitors for each of these visits or implanted with an event recorder which will be evaluated for the specific 7 day period coinciding with a visit. AF recurrence will not be counted within a 3 month blanking period following the cardiac ablation procedure.

AF Recurrence is defined as episodes lasting longer than 30 seconds in duration. To count as a study-related recurrence, the AF episode must be documented. For this study, AF also includes (documented ≥30 seconds) atrial flutter and atrial tachycardia.

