7.4.2.3 AF Recurrence

The primary endpoint will evaluate recurrence of AF during the 9 months following the blanking period. Secondarily, the recurrence of AF based on electrocardiographic data at 3 months, 6 months and 24 months will also be reported.

Assessment of the AF recurrence will be determined through evaluation of 12 lead ECG recordings, holter monitoring or event recorder results. AF Recurrence is defined as episodes lasting longer than 30 seconds in duration. To count as a study-related recurrence, the AF episode must be documented. For this study, AF recurrence also includes (documented ≥30 seconds) atrial flutter and atrial tachycardia.

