#### 2.4 Primary objective

The primary objective is to assess the feasibility of concomitant cardiac ablation for the treatment of atrial fibrillation and renal denervation ablation using the EnligHTN renal denervation system in achieving freedom from atrial fibrillation in patients with hypertension.

Project Code: SJM-CIP-0009 Project Name: RD+AF

The freedom from atrial fibrillation will be assessed based on electrocardiographic data during nine months following the blanking period including the one week recording coinciding with the 12 month follow-up visit (9 months following the 3 month blanking period). AF recurrence during the blanking period will not qualify as an endpoint event per protocol. Subjects may be re-treated with up to two repeat ablation procedures during the course of the study with a 3 month blanking period following the treatment. Assessment of the AF recurrence will be determined through evaluation of 12 lead ECG recordings, holter monitoring or event recorder results. AF Recurrence is defined as episodes lasting longer than 30 seconds in duration unless detected via 12-lead EKG. To count as a study-related recurrence, the AF episode must be documented on the AF Recurrence Evaluation CRF. For this study, AF also includes (documented >30 seconds) atrial flutter and atrial tachycardia.

No formal hypothesis testing will be performed. An overall percentage of subjects experiencing an event will be summarized for each randomization arm and is defined as:

Number of subjects with AF recurrence within 12 months post procedure Number of subjects with at least 12 months of follow – up or experienced AF recurrence \* 100

Subjects who exit the study prior to 12 month visit without AF recurrence will be excluded from the percentage to prevent under-estimation of the event rate. Kaplan-Meier analysis may be performed to provide freedom from atrial fibrillation rates at one year for each randomization arm using date of ablation procedure to date of first event.

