#### 2.5.3 AF Recurrence

The primary endpoint will evaluate recurrence of AF during the 9 months following the blanking period for each group. Secondarily, the recurrence of AF based on electrocardiographic data at 3 months, 6 months and 24 months post procedure will also be reported by group. The rate of AF recurrence will be calculated using the same definition as the primary objective for the specified time points.

 Assessment of the AF recurrence will be determined through evaluation of 12 lead ECG recordings, holter monitoring or event recorder results. AF Recurrence is defined as episodes lasting longer than 30 seconds in duration unless detected via 12 Lead EKG. To count as a study-related recurrence, the AF episode must be documented. For this study, AF recurrence also includes (documented ≥30 seconds) atrial flutter and atrial tachycardia.

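### The AF recurrence percentage keeps recurrent early exits but drops AF-free ones, Kaplan-Meier is optional at one year and absent at 24 months, and the 3-month rate is essentially 0% by definition

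*SAP*

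**What the plan says.** SAP 2.4 defines the primary percentage for each arm. The numerator is "Number of subjects with AF recurrence within 12 months post procedure". The denominator is everyone followed for 12 months plus anyone who recurred. Subjects that "exit the study prior to 12 month visit without AF recurrence will be excluded from the percentage to prevent under-estimation of the event rate". As an option, "Kaplan-Meier analysis may be performed to provide freedom from atrial fibrillation rates at one year for each randomization arm".

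For the secondary time points, SAP 2.5.3 says that "the recurrence of AF based on electrocardiographic data at 3 months, 6 months and 24 months post procedure will also be reported by group" and that "The rate of AF recurrence will be calculated using the same definition as the primary objective for the specified time points". It does not mention Kaplan-Meier. Protocol 7.4.2.3 likewise says that "the recurrence of AF based on electrocardiographic data at 3 months, 6 months and 24 months will also be reported".

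On blanking, SAP 2.4 says that "AF recurrence during the blanking period will not qualify as an endpoint event per protocol". Protocol 4.6 sets the period at three months and says that recurrences in it are not reported.

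On detection, protocol 4.10.10 says: "Assessment of AF Recurrence will be completed at the 3M, 6M, 12M and 24M follow-up visits". Even an implanted recorder is read only for the 7 days around a visit.

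**The concern.** The denominator treats two leavers with the same follow-up differently. A subject whose recurrence is found at the 6-month visit and who leaves at month 8 is counted. A subject who is AF-free at 6 months and leaves at month 8 is removed. If leaving has nothing to do with AF, the counted group is enriched with recurrences. More subjects do not cure this, and the size differs between arms if drop-out differs. No hypothesis test is planned, so the reported percentages are the result.

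Kaplan-Meier handles both leavers consistently if exit is unrelated to AF. The SAP leaves it optional for AF at one year and does not mention it at 24 months, although the AF objective in protocol 3.2 runs to 2 years. SAP 2.5.2 does offer it for major adverse cardiac events, which are summarized to 2 years, so the gap for AF does not look like a matter of principle.

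The 3-month rate is a separate matter. A value near 0% in both arms could be read as a finding, although the definition fixes it.

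**Working it through.** **Inputs.** The plan states no drop-out rate and no expected recurrence rate, so it has no figure of its own to reproduce. From the documents: the SAP 2.4 formula, a 3-month blanking period, scored visits at 6, 12 and 24 months, and arms of 50 and 25 (75 subjects at 2:1, SAP 2.2). Protocol 7.2 says about 100, which would narrow the intervals somewhat. Assumed: exit of d = 10, 20 or 30% by time point T, evenly spread and unrelated to AF; true recurrence 40% at 12 months and 50% at 24 months; 20% at 6 months for a separate 6-month bound. These are separate illustrations, not one population.

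**Formula, recurrence found only at visits.** Let F be cumulative recurrence at each visit and S = (1−d)^(t/T) the share not yet exited. Counted recurrences are N = Σ(F_k − F_(k−1))·S_k, AF-free completers are C = (1−F_T)·S_T, and the SAP percentage is N/(N+C).

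**12 months, d = 20%.** A constant hazard from month 3 gives F6 = 1 − 0.6^(1/3) = 0.157, with F12 = 0.40.
- N = 0.157×0.894 + 0.243×0.8 = 0.335; C = 0.6×0.8 = 0.48.
- SAP percentage = 0.335/0.815 = 41.1%, a shift of +1.1 points.
- Removed: 1 − 0.815 = 0.185 of subjects, of whom (0.400 − 0.335)/0.185 = 35% truly recur by month 12. That is below 41.1%, so removing them raises the rate. Had more than 41.1% of them been recurrent, the percentage would be too low.
- Keeping everyone in the denominator gives 33.5%, or −6.5 points.
- Bounds: all removed subjects AF-free, 33.5%; all recurrent, 1 − 0.48 = 52.0%.

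**Continuous detection.** λ = −ln(1−p)/(T−3), μ = −ln(1−d)/T, E = ∫ from 3 to T of λ·exp(−λ(t−3))·exp(−μt)dt, percentage = E/(E + (1−p)(1−d)).

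| Shift in points | d = 10% | 20% | 30% |
|---|---|---|---|
| 12 months, visits only | +0.5 | +1.1 | +1.8 |
| 12 months, continuous detection | +1.0 | +2.2 | +3.6 |
| 12 months, visits only, all exits between the 6- and 12-month visits | +1.0 | +2.3 | +3.8 |
| 6 months, visits only | 0 | 0 | 0 |
| 6 months, continuous detection (true 20%) | +0.4 | +1.0 | +1.5 |
| 24 months, visits only, constant hazard (F = 0.094/0.257/0.50) | +0.8 | +1.8 | +2.9 |
| 24 months, visits only, 40% recurred by month 12 (F = 0.157/0.40/0.50) | +1.3 | +2.7 | +4.4 |

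The continuous rows are upper bounds for evenly spread exit. If all exits precede the 6-month visit, the visits-only shift at 12 months is 0.

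**Near saturation.** In the prior study in protocol section 2, 10 of 14 ablation-only patients (71.4%) were not AF-free at 12 months. With that hazard unchanged (F = 0.341/0.714/0.946) and visits only, 10% exit gives +0.5 at 12 months. At 24 months it gives +0.25 (10% exit in total) to +0.5 (10% per year).

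**Unequal exit, 10% against 30%, same true rate.** The spurious gap is 1.8 − 0.5 = 1.3 points at 12 months (3.6 − 1.0 = 2.6 under continuous detection). At 24 months it is 2.9 − 0.8 = 2.1 to 4.4 − 1.3 = 3.1.

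**Scale.** 95% half-widths at 40%: 1.96·√(0.24/50) = 13.6, 1.96·√(0.24/25) = 19.2, and for the difference √(13.6² + 19.2²) = 23.5 points.

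**3 months.** Blanking runs to month 3 and episodes in it do not qualify, so the numerator is essentially empty. The exceptions are a 3-month visit held up to 10 days late and a repeat ablation during blanking, which protocol 4.8 counts towards recurrence.

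**Check of the remedy.** In simulation (4,000 replicates, n = 50 and 25, 20 or 30% exit by month 24, visits at nominal times, 0 or 50% of recurrences documented between visits), Kaplan-Meier as set out under the fix gave 39.8–40.1% at 12 months and 49.8–50.2% at 24. The SAP percentage gave 40.3–41.4% and 52.5–54.9%. When visits vary within their windows, Kaplan-Meier on actual dates read at exactly 12 months gave about 30% against a true 40%, because many 12-month visits fall after that day. Nominal visit times gave 39.7%.

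**The case against.** The best defence is that the exclusion is deliberate and its reason sound. Data collection stops at withdrawal (protocol 4.11), and the all-subjects percentage errs further the other way (−6.5 against +1.1 points at 20% exit). The study is a descriptive feasibility study with no decision rule, the 12-month shift is far below sampling error, Kaplan-Meier at one year is already named, and ad hoc analyses are allowed. Every size above rests on assumed drop-out and recurrence. All of this stands, and it keeps the point minor. It does not answer the missing Kaplan-Meier at 24 months or the 3-month rate.

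A reader might infer more than the documents support:
- *The bias is always upward.* It is upward only if exit is unrelated to AF and falls after the first scored visit. Kaplan-Meier needs the same assumption about exit.
- *The shift is always larger at 24 months.* It usually is, but not when recurrence is near saturation by month 12.
- *The 6-month shift is exactly zero.* Protocol 4.7 does not restrict recurrences to visits, 4.8 counts repeat ablations, 4.11 asks for an ECG at withdrawal, and SAP 2.4 asks only for documentation on the recurrence form. Some events can therefore be documented between visits.

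**Conclusion.** The point holds as a minor one. The SAP percentage is asymmetric, and under exit unrelated to AF it overstates recurrence slightly at 12 months and usually somewhat more at 24 months, where no alternative estimate is planned. The sizes are conditional on 10 to 30% exit and true rates of 40% and 50%; with no exits the shift is nil. It would be wrong to conclude that the primary 12-month result is materially distorted, or that the exclusion is worse than counting leavers as AF-free. The 3-month part needs no assumption about drop-out: two provisions of the plan leave that rate almost nothing to count.

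**What to change.** In SAP 2.4 and 2.5.3:

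1. Make Kaplan-Meier per arm, with 95% confidence intervals, the required estimate at 12 and 24 months.
2. Censor AF-free exits at the date their follow-up ended.
3. Count a visit inside its window as that visit. Place visit-detected events and the censoring of AF-free completers at the nominal visit time, and read the curve there. Events documented between visits keep their own date.
4. Keep the percentage as supportive, with the number and timing of exclusions per arm.
5. State that Kaplan-Meier assumes exit unrelated to AF, and show the bounds with all excluded subjects counted as AF-free and then as recurrent.
6. Remove the 3-month recurrence rate from SAP 2.5.3 and protocol 7.4.2.3 together, so that the documents agree. The 3-month visit and its recording stay.

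The cost is SAP wording, a one-line protocol change and slightly more programming. The downside of step 3 is that exact visit dates are lost, and subjects seen early in the window are credited with up to 21 days (12-month visit) or 60 days (24-month visit) of unobserved AF-free time.

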#### 2.5 The Secondary objectives

#### 2.5.1 Safety Acute data

The major adverse cardiac events (MACE) within 7 days post procedure will be summarized as a percentage of patients as defined as:

Number of subjects with major adverse cardiac events within 7 days post procedure Number of subjects with at least 7 days of follow – up or who experienced an event \* 100

The denominator includes subjects who either had an event within 7 days post procedure or were eligible to meet the endpoint, i.e. followed through at least 7 days.

The peri-procedural events will be summarized as a percentage of patients as described below. Rates will be calculated for each randomization arm.

Number of subjects with at least one event within 30 days post procedure Number of subjects with at least 30 days of follow – up or who experienced an event \* 100

All serious and possibly device or procedure related adverse events are reported and adjudicated by an internal medical expert. An event is considered a MACE if it meets the criteria defined in the Adverse Event Adjudication Plan.

#### 2.5.2 Safety Midterm (6 months) and Long term (1-2 years) data

For all patients, the major adverse cardiac events will be recorded and summarized at 6 months, 1 year, and 2 years. Event rates will be calculated for each arm as the number of subjects who experienced a major adverse cardiac event over the number of subjects who experienced an event within or were followed to each time interval. Kaplan-Meier analysis may be performed for time to first major adverse cardiac event. For patients undergoing the renal denervation procedure:

The new (or worsened) renal artery stenosis (>50%) and/or aneurysm at the site of

- ablation per Renal Artery Imaging will be summarized at 6 and 12 months. A percentage of patients who have new stenosis and/or aneurysm compared to baseline will be provided. The denominator includes subjects with a baseline and follow-up assessment at the corresponding interval. Image interpretation will be based on local analysis. Kaplan-Meier analysis may be performed if applicable on the time to the first new renal artery stenosis and/or aneurysm at the site of ablation.
- Renal function change based on eGFR will be summarized by computing the change of the eGFR at 6 months, 12 months and 2 years compared to baseline (follow-up interval baseline) for each patient with data available in both time points. The mean and standard deviation of the eGFR change at those intervals will be presented.
- Overall renal vascular safety will be summarized as a rate of subjects with a serious, device or procedure related event over total subjects randomized to the renal denervation group at each follow-up time point.

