4.11 Clinical Investigation Termination

Each subject will be followed for 2 years post ablation procedure or until time of death, loss to follow up, withdrawal or clinical investigation termination. The clinical investigation will be complete after all follow-up visits are performed, all data is received by the Sponsor and the database is locked. The study will be closed when a final report is written on the conclusions and analysis of the data.

Participation in this clinical investigation is voluntary. Subjects are free to withdraw from the clinical investigation at any time without reason. However, subjects should be strongly encouraged to complete the protocol required follow up. Should a subject wish to withdraw prior to completing 60-month follow-up, the investigator should request the subject to come in for a final visit and a Termination CRF should be completed by the site and provided to the Sponsor.

At this visit the subject should undergo the following evaluations:

• Office Blood Pressure measurement

- Blood/Urine labs
- 12 Lead ECG

In a situation where a clinical investigation withdrawal is due to an adverse event the subject should be followed until resolution of that adverse event or determination that the subject's condition is stable. Upon withdrawal from the study, data will cease to be collected on Case Report Forms.

Subjects must be informed about their right to withdraw from the investigation at any time and for any reason without sanction, penalty or loss of benefits to which the subject is otherwise entitled and withdrawal from the investigation will not jeopardize their future medical care or relationship with the investigator. Subjects will be asked to specify the reason for the withdrawal, but have the right not to answer.

The investigator may decide to withdraw a subject from the investigation at any time. The subject's future care will not be influenced by a decision, voluntary or otherwise, to withdraw from the investigation. All reasonable efforts should be made to retain the subject in the clinical investigation until completion of the investigation.

Reasons for termination include, but are not limited to, the following:

- Subject did not meet the inclusion/exclusion criteria
- Subject requests to be withdrawn from the study
- Investigator withdraws subject from the study
- Subject lost to follow-up, defined as the following: a subject will be considered

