5.7.7 Anticipated Serious Adverse Device Effect (ASADE)

A serious adverse device effect which by its nature, incidence, severity or outcome has been previously identified in the risk analysis report.

5.7.8 Procedure for assessing, recording and reporting adverse events, adverse device effects, serious adverse events and serious adverse device effects:

Safety surveillance and reporting will be done for all subjects enrolled in this investigation as described below.

Safety surveillance within this investigation and the safety reporting performed by the investigator, starts as soon as the subject is enrolled in this investigation (date of signature of the informed consent). The safety surveillance and the safety reporting will continue until the last

investigational visit has been performed or the subject is deceased or the subject/investigator concludes his participation into the investigation.

For the purpose of this trial, all Serious Adverse Events and all Adverse Device Effects (regardless of severity) are to be documented and reported to the sponsor immediately and this no later than 72 hours after becoming aware of the event.

Adverse events will be assessed by the investigator for relationship to the device and to the procedures involved.

- Procedure related: The AE is deemed related to the procedure if it occurred during the procedure but was not directly caused by the medical device.
- Device related: The AE is deemed device related if it was directly caused by the medical device.

Investigators are responsible for promptly reporting all SAEs and ADEs to the sponsor by completing the Adverse Event form. All unresolved AEs should be followed by the investigator until resolution is reached.

Note: Refer to Table 1 'Data Collection' and Appendix G 'Data Collection Method'. In case of EDC failure, notify Sponsor via Fax ([contact]) or via [contact].

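### At 24 months the SAP's follow-up formula and its visit-based exclusion sentence give different denominators; the formula inflates AF recurrence, and 2-year MACE too if read as a day count

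*SAP*

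**What the plan says.** **AF recurrence.** The denominator of the formula in SAP 2.4 is "Number of subjects with at least 12 months of follow – up or experienced AF recurrence". Directly below it, the SAP states the exclusion in terms of a visit: "Subjects who exit the study prior to 12 month visit without AF recurrence will be excluded from the percentage". SAP 2.5.3 extends the rule to 3, 6 and 24 months: "The rate of AF recurrence will be calculated using the same definition as the primary objective for the specified time points".

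**MACE.** SAP 2.5.2 has these events "summarized at 6 months, 1 year, and 2 years", with a denominator of "the number of subjects who experienced an event within or were followed to each time interval". It gives no day count and no link to a visit window.

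**End of follow-up.** Protocol 4.11 says "Each subject will be followed for 2 years post ablation procedure". Protocol 4.10 and Tables 1 and 2 allow the 24-month visit a window of ±60 days, and no later visit is scheduled. Protocol 5.7.8 ends safety reporting there: "The safety surveillance and the safety reporting will continue until the last" "investigational visit has been performed or the subject is deceased" (one sentence, split by a page break), or when participation otherwise ends.

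**Time-to-event analysis.** Kaplan-Meier is optional for MACE (SAP 2.5.2). For AF it is also optional, and is named only for one-year rates (SAP 2.4).

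**The concern.** A subject who attends the last visit on day 680 without a recurrence has done everything the protocol asks, yet has less than 24 months of follow-up. The formula drops this subject. The exclusion sentence keeps the subject, because the visit took place. A subject seen on the same day who has had a recurrence counts under both rules. The loss therefore falls only on event-free subjects and can only push the rate up.

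The 6- and 12-month rates are largely spared, since a subject seen early at those visits normally stays in the study and accrues the remaining days. At 24 months nothing follows.

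No hypothesis test is planned (SAP 2.2), so these percentages are themselves the 2-year result. Two programmers working from the same SAP could report materially different figures.

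**Working it through.** **Inputs from the documents**
- 24-month visit window: ±60 days (Protocol 4.10, Tables 1 and 2).
- Renal denervation arm: at least 50 subjects (SAP 2.2). This agrees with the SAP's total of 75: 75 × 2/3 = 50.
- The plan states no expected 2-year rate, so there is no planned rate to reproduce.

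**Assumptions**
- 24 months = 730 days. The window then runs from 730 − 60 = day 670 to 730 + 60 = day 790.
- e = subjects with an event; n = subjects with an event or who attend the 24-month visit; f = share of event-free completers last seen before day 730. The documents give neither e nor f. If last visits were spread evenly over the 121 days of the window, 60/121 = 49.6% would fall before day 730, so f = 50% is used as an upper illustration.

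**Formulas**
- Visit-based rule: rate = e / n, whatever f is.
- Day-count rule: rate = e / (e + (n − e)(1 − f)).

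Example with n = 50 and e = 5. Visit-based: 5/50 = 10.0%. Day count:
- f = 10%: 5 / (5 + 45 × 0.90) = 5/45.5 = 11.0%
- f = 25%: 5 / (5 + 45 × 0.75) = 5/38.75 = 12.9%
- f = 50%: 5 / (5 + 45 × 0.50) = 5/27.5 = 18.2%

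For other rates with n = 50:

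| Visit-based rate | f = 10% | f = 25% | f = 50% |
|---|---|---|---|
| 5/50 = 10.0% | 11.0% | 12.9% | 18.2% |
| 10/50 = 20.0% | 21.7% | 25.0% | 33.3% |
| 20/50 = 40.0% | 42.6% | 47.1% | 57.1% |

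Only the ratio e/n matters, so the percentages do not depend on the choice of n. At f = 0 the two rules agree.

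**Bias of the visit-based rule.** It treats an early completer as fully observed and so misses events between the last visit and day 730. In the extreme case, with every completer last seen on day 670 and a constant hazard, the observed rate is 1 − (1 − p)^(670/730). True rates of 10%, 20% and 40% would read 9.2%, 18.5% and 37.4%. Apart from very small f, this is the lesser error: at a 10% rate it is 0.8 points downward, against 2.9 points upward at f = 25% and 8.2 points at f = 50%.

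**The case against.** The best defence is that the SAP already has the right rule. The sentence under the AF formula can be read as explaining it. Carried to 24 months, it removes only subjects who leave before that visit, so the day-680 completer stays in. For MACE, the wording contains no month or day threshold, and the same section uses the word interval for scheduled assessments. Where the SAP wants a day count it states one, as for the 7-day and 30-day rates in SAP 2.5.1. The share of early visits is unknown and may be small.

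Most of this stands. Inflation is a consequence of one reading, and for MACE the visit-based reading is at least as natural. It does not remove the AF problem, because the formula is the stated calculation, it sets a minimum follow-up time, and nothing says that the sentence below overrides it.

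Three stronger conclusions might be inferred, and the documents do not support them:
- *That the 2-year safety rates in general are inflated.* Of those summaries only MACE is exposed. Stenosis and aneurysm are reported at 6 and 12 months only, eGFR change uses subjects with both measurements, and overall renal vascular safety divides by all subjects randomized to renal denervation (SAP 2.5.2).
- *That a false difference between arms follows.* Both arms share one schedule and window, randomization is stratified by site (Protocol 3.4), and nothing suggests that last-visit timing differs by arm. With equal underlying rates and equal f, both arms would read the same inflated figure.
- *That the ±60-day window is itself an error.* It is a design choice; the fault is that the SAP does not say how follow-up time is judged against it.

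**Conclusion.** The point holds in conditional form. At 24 months the AF formula and the sentence beneath it define different denominators, and the formula as written biases AF recurrence upward. The 2-year MACE rate is affected only if its denominator is read as a day count.

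The size rests on f, which the documents do not give. A 10% rate would read 11.0% to 18.2% for f between 10% and 50%, and a 40% rate 42.6% to 57.1%. The inflation is zero if no event-free completer is seen before day 730, or if the visit-based rule is used. A reader might take the upper figures as the expected bias. They are illustrations that need both the day-count reading and about half of last visits falling early. The case for acting is that the SAP leaves the choice open and closing it costs almost nothing.

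**What to change.** In SAP 2.4, 2.5.2 and 2.5.3, count a subject as followed to 24 months if the 24-month visit was completed on day 670 or later, including visits made after the window closes on day 790. Reword the denominator in SAP 2.4 so that it matches its own visit-based exclusion sentence.

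The cost is about one sentence in each place, with no protocol amendment and no burden on subjects. The downside is the slight downward bias shown above (a true 10% reads about 9.2% in the extreme case). Reporting a 2-year Kaplan-Meier estimate alongside the percentage would address this, provided that enough subjects are followed to day 730. The method is already listed as optional for MACE; for AF it would need to be extended from one year to two.

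Changing the visit window, or adding an event contact on or after day 730, is optional and is not needed to settle the denominator.

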4.10.9 Renal artery evaluation

The renal artery evaluation will only be done in subjects who underwent the renal denervation ablation procedure.

Renal artery evaluation will be completed at the 6M and 12M follow-up visits. This evaluation can be completed by either: computed axial tomography (CT scan), duplex ultrasonography, Doppler, angiography, magnetic resonance (MR) angiography or non contrast magnetic resonance imaging.

If a renal artery evaluation is completed at any other time point during the study, this data will also be collected in the Renal Artery Evaluation CRF.

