7.4.2.2 Safety Midterm (6 months) and Long term (1-2 years) data

For all patients, the major adverse cardiac events will be recorded.

For patients undergoing the renal denervation procedure:

- The new renal artery stenosis (>50%) and/or aneurysm at the site of ablation per Renal Artery Imaging will be summarized at 6 and 12 months as percentage of patients who have stenosis and/or aneurysm. Image interpretation will be based on local analysis. Kaplanmeier analysis may be performed on the time to the first new renal artery stenosis and/or aneurysm at the site of ablation
- Renal function change based on eGFR will be summarized by:

- 1. Computing the change of the eGFR at 6 months, 12 months and 2 years compared to baseline for each patient with data available in both time points.
- 2. Calculating the mean and standard deviation of the eGFR change at those intervals

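### The 6- and 12-month renal stenosis/aneurysm percentage has no clause keeping subjects who already had the event, so lesions found off schedule or treated before the visit can be lost and the rate understated

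*SAP*

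**What the plan says.** Protocol 3.2 makes renovascular safety, measured by new renal artery stenosis or aneurysm at the ablation site, a secondary objective at 6 and 12 months. On imaging, Protocol 4.10.9 says "Renal artery evaluation will be completed at the 6M and 12M follow-up visits", in denervated subjects only. It adds: "If a renal artery evaluation is completed at any other time point during the study, this data will also be collected", on the same case report form.

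Protocol 7.4.2.2 says the finding "will be summarized at 6 and 12 months as percentage of patients who have stenosis and/or aneurysm" and gives no denominator. SAP 2.5.2 supplies one. The numerator is described by "A percentage of patients who have new stenosis and/or aneurysm compared to baseline will be provided" and the denominator by "The denominator includes subjects with a baseline and follow-up assessment at the corresponding interval".

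The same SAP builds its other event rates differently:

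- 7-day MACE (SAP 2.5.1): "The denominator includes subjects who either had an event within 7 days post procedure or were eligible to meet the endpoint". The 30-day peri-procedural rate has the same form.
- MACE at 6 months, 1 year and 2 years (SAP 2.5.2): events "over the number of subjects who experienced an event within or were followed to each time interval".
- AF recurrence (SAP 2.4): 12 months of follow-up or a recurrence. The SAP explains its exclusion of early leavers without recurrence as a guard against underestimating the rate.

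Two other summaries in SAP 2.5.2 bear on the point. A Kaplan-Meier analysis of time to first new lesion is optional. A rate of serious device- or procedure-related renal vascular events, over all subjects randomized to denervation, is planned.

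**The concern.** Unscheduled renal imaging may well be prompted by a suspected problem, so a scan outside the 6- and 12-month visits is more likely than a routine one to be positive. The plan collects these scans but does not say whether they count. Two kinds of case are exposed:

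- **Lesion found off schedule, no scan at the visit.** The subject does not meet the denominator rule and leaves numerator and denominator together.
- **Lesion found and treated, visit scan clean.** The subject stays in the denominator. Compared with baseline, the visit scan shows nothing new, and no rule says whether the earlier lesion counts.

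This is the device-specific renovascular safety result. In an arm of about 50, one or two lost cases can decide whether the report shows zero or a non-zero rate.

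**Working it through.** **Inputs.** SAP 2.2 gives 75 subjects and at least 50 (or 2/3) with denervation: 75 × 2/3 = 50, which reproduces. Protocol 7.2 gives about 100 subjects: 100 × 2/3 = 66.7, or 67. I use 50 and show 67 for range. Neither document states an expected lesion rate, an unscheduled-scan rate or a missed-scan rate, so every lesion count below is an assumption.

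**Notation.** s = subjects with a lesion seen at the visit scan; d = subjects with a lesion lost to the rule; f = lesion-free subjects scanned at the visit.

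- (a) SAP rule, lost subjects have no visit scan: s / (s + f)
- (b) SAP rule, lost subjects have a clean visit scan after treatment: s / (s + f + d)
- (c) Event-or-scanned rule: (s + d) / (s + d + f)

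**Direction against rule (c).** (c) − (a) = d·f / [(s + f)(s + d + f)] and (c) − (b) = d / (s + d + f). Neither is negative. Each is positive whenever a lesion is lost (the first also needs f > 0).

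**Size, all lesion-free subjects scanned** (exact Clopper-Pearson 95% intervals):

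| Arm | s | d | (a) | (b) | (c) |
|---|---|---|---|---|---|
| 50 | 0 | 1 | 0/49 = 0% (0 to 7.3) | 0/50 = 0% (0 to 7.1) | 1/50 = 2.0% (0.05 to 10.6) |
| 50 | 0 | 2 | 0/48 = 0% (0 to 7.4) | 0/50 = 0% (0 to 7.1) | 2/50 = 4.0% (0.5 to 13.7) |
| 50 | 1 | 2 | 1/48 = 2.1% | 1/50 = 2.0% | 3/50 = 6.0% (1.3 to 16.5) |
| 67 | 0 | 1 | 0/66 = 0% | 0/67 = 0% | 1/67 = 1.5% |
| 67 | 1 | 2 | 1/65 = 1.5% | 1/67 = 1.5% | 3/67 = 4.5% |

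Each lost lesion costs about 2 percentage points with 50 subjects and about 1.5 with 67.

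**With about 20% of lesion-free subjects unscanned, arm of 50.**

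- s = 0, d = 1: 49 lesion-free, 10 unscanned, f = 39. Rule (a) 0/39 = 0%; rule (c) 1/40 = 2.5%; over all treated 1/50 = 2.0%.
- s = 2, d = 1: 47 lesion-free, 9 unscanned, f = 38. Rule (a) 2/40 = 5.0%; rule (c) 3/41 = 7.3%; over all treated 3/50 = 6.0%.
- s = 2, d = 0: 48 lesion-free, 10 unscanned, f = 38. Rules (a) and (c) both 2/40 = 5.0%; over all treated 2/50 = 4.0%.

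So the SAP rule is never above rule (c), but against a rate over all treated subjects it can fall on either side.

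**The case against.** The strongest reply is that the SAP never limits the numerator to scheduled scans and does not define the interval. In the same section, the MACE rule uses the word for the period up to the time point ("over the number of subjects who experienced an event within or were followed to each time interval"). Read that way, a month-4 scan belongs to the 6-month interval and nothing is lost. This stands as far as it goes: a reader might infer that only scans at the two visits count, and the text does not say so outright. But renal imaging is scheduled only at those visits, so the visit is the natural reading. The other reading is not stated either, and the analyst would have to choose.

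The planned renal vascular safety rate needs no scan and uses all subjects randomized to denervation. A symptomatic or treated stenosis could well appear there. It covers only serious, related events, however, so a non-serious stenosis above 50% found incidentally need not. Protocol 5.7.8 calls an event procedure-related only if it occurred during the procedure, so a later lesion would have to be attributed to the device. Nor is it the stenosis/aneurysm measure named in the objectives.

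It can also be said that the rule follows the SAP's convention for visit-based measures such as eGFR and blood pressure, where available data at the visit are used. That explains the wording. But those are states at a visit, whereas a new lesion is an event that can be found earlier and then treated.

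A reader might further infer that the rate is certain to be understated, or that the bias always favours the device. Neither is supported. A lesion still visible on the visit scan is counted, and a treated lesion leaves only the numerator. The fixed direction holds only against the event-or-scanned rule. That rule has its own lean: a positive off-schedule scan brings a subject in, but a negative one without a visit scan does not.

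**Conclusion.** The point holds as a gap that can understate the rate. SAP 2.5.2 requires a scan at the interval, has no event clause and gives unscheduled scans no role, against the SAP's own practice for MACE and AF recurrence. Understatement needs an off-schedule or earlier lesion together with a missing or cleared visit scan. The size is about 2 percentage points per lost lesion with 50 denervation subjects, enough to turn a non-zero rate into 0%. The figures assume the lesion counts and, in the main illustration, that every lesion-free subject was scanned. The two other summaries reduce the gap without closing it. The result is secondary and descriptive, so this is a correction that should be made before analysis, not a threat to the primary objective.

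**What to change.** In SAP 2.5.2, make the 6- and 12-month rates cumulative:

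- **Numerator:** subjects with any new >50% stenosis or aneurysm at an ablation site on any scheduled or unscheduled imaging up to the end of the visit window (Protocol 4.10: ±14 days at 6 months, ±21 days at 12 months). Such a subject remains an event at later time points even if the lesion has since been treated.
- **Denominator:** subjects with such an event, or with a baseline scan and a scan at that interval.
- **Alongside:** the number of treated subjects without an interval scan, and the rate over all treated subjects as a sensitivity figure. The event-or-scanned rate can lean slightly upward when lesion-free subjects are unscanned. The all-treated rate leans the other way, because it counts unscanned subjects with no known lesion as lesion-free.
- **Time to first lesion:** make it a planned analysis.

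The cost is SAP wording and minor analysis work. The scans are already collected on the Renal Artery Evaluation form, and no visit or clinical procedure changes. The reported rate may become slightly less favourable.
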